## 4 OVERALL DESIGN AND PLAN OF THE STUDY

### 4.1 Overview

This is a multicentre Phase II, double-blind, randomized and controlled, study of the safety and preliminary efficacy of IV IFN beta-1a compared with dexamethasone in adult patients diagnosed with COVID-19 needing hospitalization, but not invasive mechanical ventilation or high flow/presurized supplemental oxygen. The primary endpoint safety and tolerability of IV IFN beta-

1a, and primary efficacy endpoint is WHO ordinal scale for clinical improvement (WHO OSCI) score at D14. Both treatment groups will receive standard care according to current treatment guidelines, except open-label corticosteroids during study days D1-D6 (or other co-medication with potential of interacting with IFN beta-1a; [Section 5.7](#)). If the patient receives (oral or intravenous) glucocorticoids during study days D1-D6, the IMP will be discontinued, and the patient will continue with in all follow-up study assessments.

[figure not shown]
Approximately 140 subjects are planned. Patients with COVID-19 admitted to hospital will undergo screening during which written informed consent will be obtained and eligibility assessed. Not more than 48 hours may elapse between arrival to hospital and administration of the first dose of study drug. An interactive web-response system (IWRS) will be used to randomise the patients using age and gender as stratification parameters.

Following randomization, patients will be treated daily with IFN beta-1a 10 µg or dexamethasone 6 mg as an IV bolus for 6 days and will undergo daily assessments while hospitalized. The main analysis and reporting will use D14 and D28 data. D90 data will be analysed separately. Final follow-up will occur at D90 by phone or through medical records. The overall duration of the study for a patient is therefore 3 months. During the long-term follow-up periods patient care will follow normal hospital procedures, as appropriate. The study will be completed when the last patient completes D90 study assessment. The study design is summarised in [Figure 1](#).

Discontinuation criteria for individual patients and the entire study are described in [Section 4.8.1](#).

The study design incorporates an Independent Data Monitoring Committee (IDMC) that will review ongoing safety (i.e., adverse events [AEs] and serious AEs [SAEs]) and will also make recommendations to the Sponsor as described in the IDMC charter. Details of the IDMC are given in [Section 8.8](#).

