# 6 STUDY CONDUCT AND ASSESSMENTS

## 6.1 General Considerations

The study will utilize standard clinical care laboratory assessments for safety, in order to avoid excessive sampling of blood in hospitalized subjects. Complete Blood Count (CBC), White Blood Cells (WBC) differential and biochemistry, for example, will be collected from clinical routine if available; if not then these will be collected as protocol specific assessments from pre-dose D1, D2-D7, D10, D14, D28/last day in hospital. The timing of the assessments is shown in the [Table 2](#) Schedule of Procedures (below). Laboratory assessments needed for CBC, differential and chemistry should be taken on the timepoints indicated in the [Table 2](#), if not available by clinical standard of care (i.e., analyses should not be duplicated if available by clinical routine).

For the purposes of this study, study day 1 (D1) is defined as the first calendar day (from midnight to the following midnight) of treatment with IFN beta-1a or dexamethasone. All days thereafter are defined as "Dn" (e.g., D2, D3, etc.) until D28.

Baseline assessments are defined as those assessments carried out in the screening period and pre-dose D1 (before the first dose of study drug on D1). Unless withdrawn from study or discharged from the hospital, all patients will receive study drug for 6 consecutive days (D1-D6). All assessments in the period up to D28 are only to be performed when a patient is in hospital. Study assessment at D14, D28 and D90 are performed by phone call if the patient is not any longer present at the hospital, or sought through records if the patient cannot be contacted. The end of the study will be the date of last patient/last visit at D90.

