**Table 2. Schedule of procedures and assessments**

Procedure	Screening	D1 pre-dose	D1-D6	D7-D14 	D15-D27	D28 short-term follow-up 	D90 long-term follow-up (+/- 7 days)
Informed consent	X						
Inclusion/exclusion criteria	X	X					
Demographics	X						
Medical history	X						
Physical examination (incl. weight and height at screening)	X					X	
Pregnancy test in women of childbearing potential	X						
Review and documentation of available lung X-ray / CT scan	X						
Genetic sample		X 					
Randomization		X					
Administration of study drug			X				
Specimen collection  :							
MxA		X	X	X			
CD73		X	X	X			
PIMs 		X	X	X			
IFN beta		X	X	X			
ADAs		X				X	
COVID-19 test (if positive result of a test taken within the last 7 days is not available)	X						
COVID-19 for viral load PCR 		X	X	X			
Nasopharyngeal swab for virus variant analysis		X					
Biochemistry, CBC & Differential 		X	X	X		X	
Data collection from medical records:	X	X	X	X		X	X
WHO 9-point ordinal scale		X	X 	X 		X 	
Previous and concomitant medications and interventional therapies	X	X	X 	X 	X 	X 	
Clinical status assessments 		X	X	X	X	X	X
Vital signs 		X	X	X	X	X	
Adverse events 	X	X	X 	X 	X 	X 	X

*All daily assessments should be obtained at the same time as D1 pre-dose assessment (+/- 2 hours). The specimen collections and assessments at pre-dose D1 should be within 4 hours prior to the administration of study drug.*

1. *If the subject is not in the hospital, information to be collected by phone on D14 and D28*
2. *Short term follow-up; D28 or Day of discharge from hospital (whichever is earlier).*
3. *Blood collection for MxA, CD73 and PIMs will occur: pre-dose on D1, D3, D5; and on D7 for hospitalized patients (for IFN blood collection will occur: pre-dose D1, D1(5 minutes after D1 dosing), pre-dose on D3 and on D7). Blood collection for ADA will occur: pre-dose D1 and D28 or Day of discharge from hospital (whichever is earlier).*
4. *PIM = Potential Inflammatory and interferon signalling Markers on a protein and RNA level (Nanostring); DNA for genetic analyses will be extracted from the pre-dose PIM sample*

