## 6.4 Post-Discharge Assessments

Patients will be contacted at D14, D28 (if discharged; assessment window of +/- 3 days permitted, but with exact assessments for D14 and D28 conditions) and D90 (if discharged; assessment window of +/- 1 week permitted) to assess for health status, including mortality. At D14 and D28 the patient will be assessed on changes in the concomitant medications and on possible adverse events. On D90 only survival and hospital status will be collected. At the time of enrolment, subjects will be asked to provide at least two methods of contact, as well as contact information for a caregiver, to facilitate contact at Day 90. Patients who cannot be reached by phone will be mailed a follow up letter. The information is sought through records if the patient cannot be contacted.

Please see section 6.3. for patients that have been discharged from the hospital but are re-admitted due to COVID-19 before D28 to the study site.

## 6.5 Withdrawal Prior to Day 28

For patients withdrawing from the study, procedures for the last day of study involvement should be followed.

In the case of an ongoing AE, appropriate safety evaluations and/or additional tests may be performed at any time when clinically indicated at the discretion of the attending physician or Investigator, until resolution or Day 28, whichever is first. Any ongoing AEs should be followed up to resolution or Day 28, whichever is the sooner.

If the patient refuses to have any of the above assessments, or if the patient is lost to follow-up, then this should be noted in the e-CRF. If a patient is lost to follow-up, wherever possible, mortality data will be sought from alternative sources, such as the patient's local physician or available national databases and all data obtained reported as SAEs.

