#### 6.6.1.2 Definitions

Definitions of AEs and SAEs and their documentation and reporting within this study follow International Conference on Harmonisation (ICH) Good Clinical Practice, European Union, and national regulations and requirements.

An AE is defined as any untoward medical occurrence that occurs in a patient or clinical investigation subject administered a pharmaceutical product, and which does not necessarily have to have a causal relationship with this treatment. An AE can therefore be any unfavourable and unintended sign (including an abnormal laboratory finding), symptom or disease temporally associated with the use of an investigational product, whether or not considered related to the product.

All AEs up to D28 are collected. AEs occurring after D28 should be reported to the Sponsor if the Investigator considers there is a causal relationship with the study drug. All AEs up to D90, which lead to death, are reported as SAEs. Concomitant illnesses, which existed before entry into the study, will not be considered AEs unless there is any deterioration from baseline that is considered clinically relevant or significant during treatment or follow-up period until D28. All AEs must be documented, regardless of the source of identification (e.g., physical examination, laboratory assessment, ECG, reported by patient).

Pre-existing conditions will be recorded in the e-CRF on the Medical History or appropriate page. A TEAE (Treatment-Emerged Adverse Event) is defined as an AE that begins or that worsens in severity after at least one dose of study drug has been administered up to D28.

See 6.1 for the schedule of collection of adverse events

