#### 6.6.1.3.4 *Adverse events related to laboratory assessments*

Abnormal laboratory findings (e.g., biochemistry, haematology, urinalysis) or other abnormal assessments (e.g., vital signs) that are judged by the Investigator as clinically significant will, if certain requirements are met, be recorded as AEs or SAEs. Clinically significant abnormal laboratory findings or other abnormal assessments that meet the definition of an AE or SAE and are detected during the study, or are present at baseline and significantly worsen following the start of the study, will be reported as AEs or SAEs.

The Investigator will exercise their medical and scientific judgment in deciding whether an abnormal laboratory finding or other abnormal assessment is clinically significant and as such an AE.

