### 7.6.1 Adverse Events

AEs and SAEs will be coded using the current version of Medical Dictionary for Regulatory Activities (MedDRA) and will be classified by system organ classes and preferred terms. In the event that intensity or relationship of an AE to the study drug is missing, a worst-case scenario will prevail (severe in intensity or probably related). Only TEAEs (AEs that occur after the first study drug administration, that were not pre-existing or that increased in intensity) will be included in the summary tables. Counting will be performed for patients and events separately. Patients experiencing the same event more than once will have that event counted once within the corresponding system organ class and with a unique preferred term. All AEs will be included in the data listings. Listings of SAEs, of AEs leading to study drug withdrawal and of AEs leading to death will also be provided.

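### Raw TEAE counts to D28 take no account of surveillance that drops at discharge, so the arm discharged sooner would record fewer non-serious events at equal true rates

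*Protocol*

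**What the plan says.** **Counting.** Protocol 7.6.1 includes only TEAEs in the summary tables, by system organ class and preferred term: "Counting will be performed for patients and events separately". SAP section 6 likewise tabulates numbers of patients and events. Neither document gives an observed-time denominator or a split by hospital status. Protocol 7.1.1 summarises exposure and study duration by arm but does not link them to adverse events.

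**Window.** Under 6.6.1.2 a TEAE is an event that "begins or that worsens in severity after at least one dose of study drug has been administered up to D28". The window is the same whether or not the patient has gone home.

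**Surveillance in hospital.** Patients "will undergo daily assessments while hospitalized" (4.1). Under Table 2 note 8, vital signs are taken around each dose and then daily until discharge. Section 6.3.4.1 schedules bloods pre-dose on D1, on D2-D7, D10 and D14 while in hospital, and on D28 or the last hospital day.

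**Surveillance after discharge.** Section 6.1: "All assessments in the period up to D28 are only to be performed when a patient is in hospital". Table 2 note 1: "If the subject is not in the hospital, information to be collected by phone on D14 and D28". Section 6.4: "At D14 and D28 the patient will be assessed on changes in the concomitant medications and on possible adverse events", and "On D90 only survival and hospital status will be collected".

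**What becomes an event.** Laboratory and vital-sign abnormalities count only if the investigator judges them clinically significant and other requirements are met (6.6.1.3.4). Section 6.6.1.3 adds that common aberrations in this population need not be adverse events unless they require intervention, lead to stopping blinded drug or concern the investigator.

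**The concern.** Comparative safety against dexamethasone is a primary objective (Protocol 3.1), and section 2.6 says both arms' safety will be assessed equally. Yet how hard events are looked for depends on hospital status, and hospital status is part of the primary efficacy scale: scores 1-2 are explicitly out of hospital and 3-7 in hospital. If treatment shifts that scale, it also shifts the observed time behind the safety tables.

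If IFN beta-1a works as the design assumes, its non-serious TEAE counts would fall partly because its patients are watched for fewer days. If it delays discharge, the distortion runs the other way. A raw count cannot separate either case from a true difference in harm.

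**Working it through.** **Inputs from the documents.** Odds ratio 0.43, 80% power, 70 per arm, two-sided 0.05 (Protocol 7.4 and 7.2); TEAE window to D28.

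**The plan's own figure.** The proportional-odds formula is N = 12(1.960 + 0.842)² / [(ln 0.43)² × (1 − Σp̄³)] = 132.2 / (1 − Σp̄³), where p̄ are the mean category probabilities. N = 140 needs Σp̄³ = 1 − 132.2/140 ≈ 0.055. The category distribution is not given, so the figure cannot be confirmed. Three assumed distributions give power 0.788, 0.807 and 0.816 at 140; one with about 60% of patients in one category gives 0.726. The figure is attainable and not in dispute.

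**Assumptions.**
- 15%, 25% or 35% of dexamethasone patients are in hospital at D14.
- 0.43 multiplies the odds of still being in hospital at D14 on IFN. If the effect ran the other way, the arms would swap.
- The true event rate is the same in both arms.
- Detection is 1 in hospital and f after discharge.
- Deaths are ignored in the stay model.

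**Stay.** S(t) = exp[−H(t/14)^k], with H = −ln(share in hospital at D14). Shape k = 1 is exponential. Shape k = 2 is a Weibull with fewer very early discharges. Inpatient days are the integral of S from 0 to 28. Recorded events are proportional to inpatient days + f × (28 − inpatient days).

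**Worked case (25%, k = 1).** IFN odds = 0.333 × 0.43 = 0.143, so the IFN share is 0.143/1.143 = 12.5%. Daily discharge rates are −ln(0.25)/14 = 0.0990 and −ln(0.1254)/14 = 0.1483. Inpatient days are (1 − e^(−28 × 0.0990))/0.0990 = 9.5 and, likewise, 6.6. The ratio at f = 0 is 0.70. At f = 0.5 it is (6.64 + 10.68)/(9.47 + 9.27) = 0.92.

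| In hospital at D14, dexamethasone / IFN | k | Inpatient days, dexamethasone / IFN | Ratio, f = 0 | Ratio, f = 0.5 |
|---|---|---|---|---|
| 15% / 7% | 1 | 7.2 / 5.3 | 0.73 | 0.94 |
| 25% / 12.5% | 1 | 9.5 / 6.6 | 0.70 | 0.92 |
| 35% / 19% | 1 | 11.7 / 8.1 | 0.69 | 0.91 |
| 15% / 7% | 2 | 9.0 / 7.6 | 0.85 | 0.96 |
| 25% / 12.5% | 2 | 10.5 / 8.6 | 0.82 | 0.95 |
| 35% / 19% | 2 | 12.1 / 9.6 | 0.80 | 0.94 |

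**Early onset.** Weighting the days by an exponential onset density with mean 5 or 10 days gives, at f = 0, ratios of 0.80-0.86 (k = 1) and 0.89-0.94 (k = 2). At f = 0.5 they are 0.93-0.95 and 0.95-0.97.

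**Cross-check on patients with an event.** With 35% against 18.8% in hospital at D14, k = 1, true 28-day incidence 60% in both arms and f = 0.5, 44.2% of the sooner-discharged arm and 47.2% of the other are recorded with a TEAE. The ratio is exactly 1 if discharge is the same in both arms or f = 1.

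**Does a simple rate cure it?** Events per in-hospital day give a ratio of 1.00 under a constant rate. If the D1-D7 rate is three times the later rate (assumption; 35% against 18.8%, k = 1), the same rate gives 1.13 against the sooner-discharged arm. A person-time denominator therefore needs study-day windows.

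**The case against.** The strongest reply is that the best-described drug effects arise under inpatient observation in both arms. Section 2.6 puts fever 1-2 hours after dosing. Section 2.3.4 puts the neutrophil fall about three days after the first dose, with recovery within days of the last. Doses are given in hospital only (5.3). A constant 28-day rate therefore overstates the effect for these events. Exponential stay also implies that 36-56% of dexamethasone and 51-68% of IFN patients leave within six days. This stands, and it is why the early-onset and Weibull cases set the lower ends of the ranges.

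A reader might infer that all laboratory and vital-sign abnormalities become events and that none can be found after discharge. The documents do not support that. Sections 6.6.1.3 and 6.6.1.3.4 filter which abnormalities count, 6.6.1.1 takes spontaneous reports, and 6.6.1.2 documents events whatever their source. Under 6.3, COVID re-admission to the study site before D28 is an SAE, and deaths are captured to D90 (6.6.1.3.1). The zero-detection case thus covers only a filtered subset of TEAEs.

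A lower count could also be partly genuine, because discharge ends dosing and the sooner-discharged arm receives less drug. That is correct, and raw counts cannot separate the two.

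Finally, no between-arm adverse-event test is planned, onset times are recorded (6.6.1.4), all events are listed, and the SAP tabulates severe, serious and drug-related TEAEs separately. This lowers the stakes but supplies no observed-time denominator.

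**Conclusion.** The point holds for the protocol's planned 140-patient comparison. At equal true rates, and with detection lower after discharge, the arm discharged sooner records fewer non-serious TEAEs. At an odds ratio of 0.43 the deficit is about 15-31% for in-hospital-only findings at a constant rate, about 6-20% if those findings cluster early, and about 3-9% for symptomatic events at half detection. These ranges rest on assumed hospital shares, stay shapes, onset times and detection, none of which the documents give.

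Two stronger readings are tempting. One is that total TEAEs would be some 30% too low on IFN beta-1a. That needs exponential stay, a constant rate and no detection at all after discharge, and it presumes that IFN is the arm that leaves sooner. The other is that the reported safety results are distorted. SAP sections 2 and 6 record five patients dosed, set no hypotheses and present the data descriptively with listings, so the effect there is minimal.

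**What to change.** In Protocol 7.6.1:

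1. Keep the all-TEAE counts of patients and events.
2. Add supportive tables of TEAEs by study-day window (for example D1-D7, D8-D14, D15-D28) and by onset in hospital or after discharge, with patient-days observed per arm in each cell.
3. Show laboratory- and vital-sign-derived TEAEs separately, with the number of patients still sampled on each scheduled day per arm.
4. Rest the between-arm harm statement chiefly on deaths and on SAEs other than those serious only because they prolonged a hospital stay, a criterion that can be met only by inpatients. Show COVID re-admissions on their own line, since they can arise only after discharge.
5. Do not describe adverse events leading to drug discontinuation as captured alike in both settings, because dosing ends at discharge.

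The cost is a few more tables. Hospital status and event onset are already collected. Rates by setting condition on a post-randomisation state, so they are supportive only. For the five patients dosed, the existing listings suffice.

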### 7.6.2 Independent Data Monitoring Committee

An IDMC will be established for the study to monitor safety (see [Section 8.8](#)).

## 8 ETHICAL, LEGAL AND ADMINISTRATIVE ASPECTS

### 8.1 Data Quality Assurance

The Sponsor or Sponsor's designee will verify the qualifications of each Investigator, inspect the site facilities and inform the Investigator of their responsibilities and the procedures for ensuring adequate and correct documentation.

The Investigator is required to prepare and maintain adequate and accurate case histories designed to record all observations and other data pertinent to the study for each study participant. All information recorded in the e-CRF for this study must be consistent with the patients' source documentation (i.e., medical records).

#### 8.1.1 Database Management and Quality Control

All study-related data generated by site personnel will be captured electronically at each study centre using the e-CRF.

Central laboratory assays (e.g., PD, genetic analyses) will be managed by the central laboratories and results will be transferred for inclusion in the study analysis database.

Once the e-CRF clinical data have been submitted, corrections to the data fields will be captured in an audit trail. The reason for change, the name of the person who performed the change, and the time and date will be logged to provide an audit trail.

The specific procedures to be used for data entry and query resolution using the e-CRF will be provided to study sites in CRF completion instructions. In addition, site personnel will receive

training on the e-CRF. Once the source data verification is complete and all queries are closed, Data Management will freeze the e-CRF page.

## 8.2 Case Report Forms and Source Documentation

All data obtained during this study must be promptly entered in the e-CRF. All source documents from which e-CRF entries are derived should be placed in the patient's medical records. Measurements for which source documents are usually available include laboratory assessments and x-ray/CT scans.

Data that will be entered directly into the e-CRF (i.e., for which there is no prior written or electronic record) are considered to be source data.

The e-CRF entries for each patient will be checked against source documents at the study site by the CRA.

### 8.2.1 Data Collection

The Investigators (and appropriately authorised staff) will be given access to an online web-based electronic data-capture system that is compliant with US Food and Drug Administration Title 21 Code of Federal Regulations Part 11. This system is specifically designed for the collection of clinical data in electronic format. Access rights to the electronic data-capture system will be carefully controlled and configured according to each individual's role throughout the study. Only the Investigator and authorised staff will be able to enter and correct data in the e-CRF. Protocol deviations can be recorded within the e-CRF system also by the Sponsor/CRO CRA.

The e-CRF should be completed for each patient included in the study and should reflect the latest observations on the patients participating in the study. Therefore, the e-CRF is to be completed as soon as possible during or immediately after the patient's visit or assessment. The Investigator must verify that all data entries in the e-CRF are accurate and correct. If some assessments cannot be done, or if certain information is unavailable, not applicable or unknown, the Investigator should indicate this in the e-CRF.

Computerised data-check programs and manual checks will identify any data discrepancies for resolution. Corresponding queries will be generated in the system and the site will be informed online about new issues to be resolved. All discrepancies must be resolved online directly by the Investigator or by staff authorised to do this by Delegation of Authority.

After completion, the Investigator will be required to electronically sign off the clinical data.

